### 8.1.3 Removal of Subjects from Therapy or Assessment

All subjects are permitted to withdraw from participation in this study at any time and for any reason, specified or unspecified, and without prejudice. The Investigator or sponsor may terminate the subject's participation in the study at any time for reasons including the following:

1. Adverse event;
2. Intercurrent illness;
3. Non-compliance with study procedures;
4. Subject's decision;
5. Administrative reasons;
6. Lack of efficacy;
7. Investigator's opinion to protect the subject's best interest.

Any subject who withdraws because of an adverse event will be followed until the sign(s) or symptom(s) that constituted the adverse event has/have resolved or is determined to represent a stable medical condition.

A subject should be withdrawn from the trial if, in the opinion of the Investigator, it is medically necessary, or if it is the desire of the subject. If a subject does not return for a scheduled visit, every effort should be made to contact the subject and determine the subject's medical condition. In any circumstance, every effort should be made to document subject outcome, if possible.

If the subject withdraws consent, no further evaluations should be performed and no attempts should be made to collect additional data.

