#### **9.8 Dose Interruption**

As this is a study of a single dose of peramivir or placebo, guidelines for treatment interruption for drug related SAEs or toxicities are not applicable.

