### 10.2.2 Screening/Baseline Evaluation and Enrollment

Screening/baseline evaluation may be conducted in the investigator's office or clinic, or in the subject's home, in which case all evaluations must be conducted by appropriately trained and qualified staff.

Clinical laboratory assessments performed at Screening are for the purpose of establishing a baseline. Subjects may be enrolled and receive treatment with study drug prior to receiving results of the laboratory assessments (with the exception of urine pregnancy test result, which must be known).

Eligible subjects will be enrolled and randomized to blinded study treatment. The randomization will be stratified by smoking status and RAT test for influenza A or B. The Investigator will prepare a request for blinded study drug assignment which includes the subject's screening number. The Investigator or designee at the clinical study center will contact the central randomization Interactive Voice System (IVRS call center). The IVRS call center will advise the study center of the investigational study drug kit number that is assigned to that subject at enrollment.

Subjects that are determined to be ineligible will be advised accordingly, and the reason for ineligibility will be discussed. If desired by the subject the reason for ineligibility may be provided and/or discussed with their health-care provider by the Investigator or designee.

Ineligible subjects who have been screened for the study will also be entered on the IVRS. For such subjects, the screening number assigned, subject's date of birth and a reason for ineligibility will be entered on to the IVRS. **All ineligible subjects must be entered onto the IVRS within 24 hours of screening**, to assist with surveillance analysis during the course of the study.

## 10.3 Treatment Period—Study Day 1

Day 1 represents the only day of study drug dosing. Study drug administration should occur as soon as possible following informed consent, screening and randomization. Therefore, it is

expected that the date of Screening/ Baseline and Day 1 will usually be the same date.

### 10.3.1 Pre-dose Evaluations-Study Day 1

Following an explanation of the Subject Self Assessment measures (Section 10.1.11), the subject shall complete the record of these assessments in their Study Diary prior to dosing. The subject will be counseled regarding the expectations for recording these assessments through Day 14.

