### **12.10.4 Missing Data**

Every effort will be made to obtain required data at each scheduled evaluation from all subjects who have been randomized. No attempt will be made retrospectively to obtain missing subject reported data (including influenza symptom severity assessments, temperature, ability to perform usual activities, missed days of work and impact of influenza on subject's work performance and/or productivity) that has not been completed by the subject at the time of return of the subject diary to the investigative site. In situations where it is not possible to obtain all data, it may be necessary to impute missing data.

In assessing the primary efficacy endpoint, for subjects who withdraw or who do not experience alleviation of symptoms, missing data will be censored using the date of subject's last non-missing assessment of influenza symptoms. Missing assessments of influenza symptoms conservatively will be imputed as having severity above absent or mild (as failures). For the subject diary data, the following data conventions will be utilized. Missing diary completion will be imputed as 11:59 for diary entries designated as morning and 23:59 for evening and daily reported values. Select exploratory sensitivity analyses may be conducted to ascertain the effect, if any, of these methods. These sensitivity analyses are further described in the SAP. Secondary efficacy endpoints with time to event data will be censored using the date of subject's last non-missing assessment of the given endpoint.

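### Section 8.1.3 permits removal for outcome-related reasons after all dosing is complete, and nothing keeps the symptom diary running or handles the informative censoring that follows

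*Combined protocol and SAP*

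**What the plan says.** References are to protocol Version 4.0 (18 December 2007).

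- **Removal.** Section 8.1.3: "The Investigator or sponsor may terminate the subject's participation in the study at any time for reasons including the following". Seven reasons follow. They include adverse event, intercurrent illness and "Lack of efficacy".
- **Dosing.** Section 10.3: "Day 1 represents the only day of study drug dosing". Section 9.8 adds that "guidelines for treatment interruption for drug related SAEs or toxicities are not applicable".
- **Censoring.** For subjects who withdraw or do not alleviate, section 12.10.4 says "missing data will be censored using the date of subject's last non-missing assessment of influenza symptoms". Section 12.7.1 has the same rule for the primary analysis. Neither distinguishes reasons for leaving. Symptom assessments that are missing count as not alleviated. Sensitivity analyses are optional and exploratory, and their detail is left to the SAP.
- **Follow-up after removal.** Section 8.1.3 also says: "Any subject who withdraws because of an adverse event will be followed until the sign(s) or symptom(s) that constituted the adverse event has/have resolved". Reaching a stable condition likewise ends this follow-up. The section adds: "In any circumstance, every effort should be made to document subject outcome, if possible". The one explicit bar on collecting data is this: "If the subject withdraws consent, no further evaluations should be performed and no attempts should be made to collect additional data". Figure 1 has a single End of Study/Early Withdrawal column, shared with Day 14.

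**The concern.** In a multi-dose trial, a removal list of this kind chiefly governs stopping drug. Here there is no drug left to stop, so ending participation ends only the diary, visits and laboratory tests. The section does not separate the two.

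A subject removed for lack of efficacy is removed because symptoms persist, and symptom duration is the primary endpoint. Censoring at the last assessment assumes that this subject would recover like those still under observation and not yet alleviated. That is not credible for this reason, and it is doubtful for adverse event or intercurrent illness.

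Three things are at stake: the estimated medians, which become too short; power, if removals are balanced or commoner on placebo; and the secondary endpoints. Complications are compared as the percentage of subjects affected, and viral shedding is averaged through Day 9 on whatever data exist (section 12.7.2), so early removal can hide events or truncate the average.

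**Working it through.** **1. The plan's own figure.** Section 12.4 gives 300 and 150 evaluable influenza A subjects, a placebo median of 137.0 h, a 30% reduction (137.0 × 0.70 = 95.9 h), a hazard ratio of 0.70, and at least 90% log-rank power at alpha 0.05. Section 12 makes tests two-sided.

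- Events needed (Schoenfeld): (1.960 + 1.282)² / [(1/3)(2/3)(ln 0.70)²] = 10.51 / 0.02827 ≈ 372.
- Expected events with exponential times and a diary of about 336 h: placebo 1 − 2^(−336/137) = 81.7%; peramivir 1 − 2^(−336/95.9) = 91.2%. Total 150 × 0.817 + 300 × 0.912 ≈ 396.
- Power: Φ(√(396 × 0.02827) − 1.960) = Φ(1.386) = 91.7%. With 450 events it is 94.6%. The stated power reproduces.

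**2. Effect of outcome-related removal.** The documents give no rate, so these inputs are assumptions: 2-10% of an arm is removed, drawn at random from its slowest-recovering 40%, and censored at 72 h. For exponential times the slowest 40% lie beyond median × log2(2.5), about 181 h on placebo and 127 h on peramivir, so all are symptomatic at 72 h. There were 3,000 simulated trials of 300 v 150 per scenario, unstratified. Monte Carlo standard error is about 0.7 points for power, √(0.8 × 0.2/3000), and 0.3 points for a 2.5% rate.

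| Removed, placebo / peramivir | Gehan power | Log-rank power | Mean placebo median (h) | Null: two-sided rejection | Null: rejection favouring peramivir |
|---|---|---|---|---|---|
| 0 / 0 | 84.5% | 90.9% | 139 | 5.2% | 1.8% |
| 2% / 2% | 82.8% | 89.5% | 135 | 5.1% | 2.2% |
| 5% / 5% | 81.5% | 89.0% | 131 | 5.3% | 2.5% |
| 10% / 10% | 77.2% | 85.5% | 126 | 4.9% | 2.2% |
| 5% / 2% | 79.4% | 85.7% | 131 | 4.1% | 1.1% |
| 10% / 5% | 73.2% | 79.6% | 127 | 5.5% | 1.0% |
| 2% / 5% | 84.3% | 90.9% | 137 | 5.5% | 3.3% |
| 5% / 10% | 84.9% | 92.4% | 131 | 5.5% | 3.8% |

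Balanced removal shortens the placebo median by 139 − 135 = 4 h to 139 − 126 = 13 h. The 84.5% starting point reflects the Gehan test on a trial sized for the log-rank. That is a separate matter and not a cost of section 8.1.3.

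**3. Treating the removed as not alleviated to Day 14.** Censoring the same subjects at 336 h brings the placebo median back to 138 h (5% / 5%) and 137 h (10% / 10%). Gehan power is then 80.5% and 73.4%, and null rejection 4.5% and 2.8%. With 10% / 5% removed, power is 84.5%; with 5% / 10% it is 69.7%. This is deliberately pessimistic: of the slowest 40% on placebo, only 18.3/40 = 46% would still be unalleviated at 336 h. It bounds the problem but does not replace the missing diaries.

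**The case against.** **Section 8.1.3 permits and does not require.** A reader might infer that the plan stops follow-up of the sickest subjects. The documents do not support that. Nothing directs removal for persistent symptoms; section 10.4.1 requires Day 21 and, if needed, Day 28 assessment of subjects still moderately or severely ill at Day 14. Section 8.1.3 asks for outcome documentation in every case and bars data collection only when consent is withdrawn. Sections 10.4.2 and 11.2 keep unresolved adverse events under follow-up, section 11.2.3 covers serious events learned of within 30 days of leaving, and the early-withdrawal visit includes laboratory tests and the complications checklist. All of this stands.

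It does not protect the primary endpoint. The seven symptoms are not adverse events unless serious (section 11.1.1), and complications are recorded separately (section 10.1.4), so adverse event follow-up need capture neither. The best-effort sentence names no diary, visit or duration. Day 21 and 28 assessments are triggered at the Day 14 visit, which a subject removed on Day 5 may not have. Counting missing entries as failures fills gaps before the censoring time and does not extend it.

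**A false benefit.** A reader might also infer that the clause manufactures efficacy. Balanced removal leaves type I error near 5%. A shift toward peramivir appears only if more peramivir subjects are removed, and it is slight: 3.3-3.8% in that direction against a nominal 2.5%, with two-sided error 5.5%. The documents offer no mechanism for such an imbalance in a double-blind trial. If the drug works, lack of efficacy should be commoner on placebo, and that costs power.

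**What cannot be seen.** The sensitivity analyses are deferred to an SAP whose text is not in the combined document, so this problem may be addressed there. Discontinuation reasons are tabulated by arm (synopsis, Safety), so an imbalance would show, but only afterwards.

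**Conclusion.** The gap is real. The plan permits removal for reasons tied to the outcome when no treatment remains to be stopped, does not say that the diary continues, and censors regardless of reason. For lack-of-efficacy removals in particular, that is informative censoring of the primary endpoint.

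Its size and direction cannot be determined from the documents. The 4-13 h shortening of the placebo median, and the Gehan power of 83-77% (balanced) or 79-73% (more placebo removals), rest on three assumptions: removal of 2-10% per arm, at 72 h, from the slowest 40% under exponential recovery. If few subjects are removed for these reasons, the effect is negligible. The case for the change does not depend on the rate: the remedy costs little and the lost diary data cannot be recovered later.

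**What to change.** - **Section 8.1.3.** Leave the list of reasons and the investigator's clinical discretion unchanged. The list is not exhaustive, so deleting items would not close the gap. Add a sentence: because dosing is complete on Day 1, ending participation for any reason other than withdrawal of consent does not end the symptom diary, the scheduled visits and safety laboratory tests through Day 14, or the Day 21 and 28 assessments if triggered. This fits the section's existing bar on data collection, which applies to consent withdrawal alone.
- **Section 12.10.4.** Pre-specify a sensitivity analysis in which subjects removed for lack of efficacy, adverse event or intercurrent illness are treated as not alleviated through Day 14 and censored there. Present it as a pessimistic bound.

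The cost is amendment wording, a few more diaries and visits in ill subjects, and one extra analysis. The assessments are already in Figure 1 for every subject.

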## 9 TREATMENTS

### 9.1 Treatments Administered

Peramivir is an investigational drug. Peramivir for intramuscular injection is a small-volume parenteral and will be supplied as a 75mg/mL solution in sodium citrate/ citric acid buffer. The pH is approximately 3.0.

A matched placebo solution of sodium citrate/ citric acid buffer with 1.2% sodium chloride at a pH of approximately 3.0 will be supplied.

The gluteal site of injection and the syringe needle length are to be recorded in the subjects CRF. Procedures for intramuscular injection, with a recommended needle length appropriate to the physical characteristics of the subject, are provided in the study drug administration manual.

### 9.2 Identity of Investigational Product(s)

Peramivir and placebo peramivir will be supplied in clear 2mL vials. An individual study drug kit will contain 2 vials of blinded study drug (peramivir and/or placebo, depending upon the treatment group). Syringes and needles will be provided in which to draw up the solution for intramuscular injection. All study drug kits must be stored at 2-8°C.

Each individual study drug kit will be labeled with some or all of the following information as required by local regulations:

- Sponsor name and contact information, study protocol number, kit number, description of the contents of the container, instructions for the preparation of the syringe and administration of the study drug, conditions for storage, statement regarding the investigational (clinical trial) use of the study drug and date for retest or expiry date.

Each vial of study drug will be labeled with some or all of the following information as required by local regulations:

- Sponsor name, study protocol number, description of the contents of the vial, instructions for the preparation of the syringe, statement regarding the investigational (clinical trial) use of the study drug and lot number.

### 9.3 Method of Assigning Subjects to Treatment Groups

Subjects will be centrally randomized in a ratio of 2:1 to a single dose peramivir 300mg or placebo, in accordance with a computer-generated randomization schedule prepared by a non-study statistician. Each subject's assignment to treatment will be stratified according to smoking status and RAT test for influenza A or B.

Once a subject is eligible for randomization, he/she will be assigned a study drug kit number that will be obtained by study staff from the study interactive voice response system (IVRS). Once a study drug kit number has been assigned to a subject, it cannot be reassigned to any other subject.

#### **9.4 Study Medication Accountability**

The Investigator/pharmacist must maintain accurate records of the disposition of all study drugs received from the sponsor, issued to the subject or directly administered to the subject (including date and time), and any drug accidentally destroyed. The sponsor will supply a specific drug-accountability form. At the end of the study, information describing study drug supplies (e.g., lot numbers) and disposition of supplies for each subject must be provided, signed by the Investigator or designee, and collected by the study monitor. If any errors or irregularities in any shipment of study medication to the site are discovered at any time, the Project Manager must be contacted immediately.

At the end of the study, all medication not dispensed or administered and packaging materials will be collected with supervision of the monitor and returned to the sponsor or destroyed on site as dictated by the appropriate Standard Operating Procedure at the participating institution.

#### **9.5 Blinding/Unblinding of Treatments**

This is a double-blind study. The treatment group assignment will not be known by the study subjects, the investigator, the clinical staff, the CRO, or Sponsor staff during the conduct of the study.

Section 11.24 provides information regarding the process for unblinding the treatment assignment, if necessary, in the event of an SAE.

#### **9.6 Prior and Concomitant Therapies**

All medications, by any route of administration, used during this study must be documented on the Case Report Form (CRF). Prescription as well as non-prescription medications should be recorded. Medication used for the treatment of influenza-related symptoms will be captured by the subject in the diary card provided by BioCryst.

#### **9.7 Overdose and Toxicity Management**

To date there is no experience with overdose of intramuscular or intravenous peramivir. If overdose occurs, subjects should receive indicated supportive therapy and evaluation of hematologic and clinical chemistry laboratory tests should be conducted. The effect of hemodialysis on elimination of peramivir is unknown.

#### **9.8 Dose Interruption**

As this is a study of a single dose of peramivir or placebo, guidelines for treatment interruption for drug related SAEs or toxicities are not applicable.

## 10 STUDY CONDUCT

A study schedule of evaluations is presented in [Figure 1](#). A detailed list of the evaluations and visits is also provided in the following sections.

### 10.1 Evaluations

All subjects enrolled in this study will undergo the following evaluations:

#### 10.1.1 Informed Consent

Prior to any study-related procedure subjects will be administered informed consent. For further discussion of consent see section [10.21](#).

#### 10.1.2 Medical History

Medical history, influenza vaccination status within the previous 12 months and demographic data (including smoking behavior) will be recorded at Screening/Baseline.

#### 10.1.3 Rapid Antigen Test for Influenza

At Screening/Baseline, a commercially available, rapid antigen test (RAT) for influenza A and B will be performed on an adequate specimen collected by swabbing the anterior nose in accordance with the RAT manufacturer's instructions. A negative initial RAT should be repeated within one hour. Refer to the Study Manual [or RAT test package insert(s)] for instructions regarding the use of the RAT kits provided for this study. Sites may use the kits provided by the Sponsor or any other commercially approved RAT available at their site to document a confirmed influenza infection.

#### 10.1.4 Physical Examination and Influenza-related Complications Assessments

The Investigator will perform a physical examination at Screening/Baseline. Subject's height and weight, and BMI will be recorded at Screening/Baseline in the subjects CRF.

Study personnel will be provided with an influenza-related complications (IRC) checklist in the CRF to evaluate the subject for the presence of clinical signs and/or symptoms of the following influenza-related complications: sinusitis, otitis, bronchitis and pneumonia. Note that subjects with clinical signs and/or symptoms consistent with otitis, bronchitis, sinusitis, and/or pneumonia at screening are not eligible for enrollment in this study (See Section [8.1.2](#) exclusion criteria number 8).

If an IRC is suspected then a targeted physical examination will be conducted to record the presence/absence of the IRC. If the investigator determines that the subject experiences (or is presumed to experience) an IRC as noted above, he/she will record that assessment on the IRC CRF page and any medication used to treat the condition will be recorded on the concomitant medication page. The investigator will promptly provide appropriate treatment for any suspected or proven IRC. Such information describing IRC signs and/or symptoms should not be reported as adverse events. Any injection site reactions noted will be recorded in the CRFs as adverse events.

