**10.4.2 Adverse Events Reported at Post-treatment Visits**

In this study, symptoms of influenza will be considered separately from adverse events reported during the post-treatment period. Accordingly, adverse events that have onset in the post-treatment period will be assessed and followed as specified in 11.2. Specifically, the investigator should attempt to follow all unresolved AEs and/or SAEs observed during the study until they are resolved, or are judged medically stable, or are otherwise medically explained.

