## 11 ADVERSE EVENT MANAGEMENT

### 11.1 Definitions

#### 11.1.1 Adverse Event

An AE is any untoward medical occurrence in a clinical study subject. No causal relationship with the study drug or with the clinical study itself is implied. An AE may be an unfavorable and unintended sign, symptom, syndrome, or illness that develops or worsens during the clinical study. Clinically relevant abnormal results of diagnostic procedures including abnormal laboratory findings (e.g., requiring unscheduled diagnostic procedures or treatment measures, or resulting in withdrawal from the study) are considered to be AEs.

AEs may be designated as “nonserious” or “serious” (see Section 11.1.2).

Surgical procedures are not AEs but may constitute therapeutic measures for conditions that require surgery. The condition for which the surgery is required is an AE, if it occurs or is detected during the study period. Planned surgical measures permitted by the clinical study protocol and the conditions(s) leading to these measures are not AEs, if the condition(s) was (were) known before the start of study treatment. In the latter case the condition should be reported as medical history.

Assessment of seven influenza symptoms (cough, sore throat, nasal obstruction, myalgia [aches and pains], headache, feverishness, and fatigue) will be documented in a subject’s study diary and analyzed as a measure of efficacy of the study treatment. These symptoms will not be reported as AEs unless the symptom(s) worsen to the extent that the outcome fulfils the definition of an SAE, which then must be recorded as such (see Section 11.1.2). Likewise, a RAT for influenza is required at screening in order to determine eligibility for the study, and therefore a positive RAT is not considered an AE.

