#### 11.1.2 Serious Adverse Event

A SAE is an adverse event that results in any of the following outcomes:

- Death
- Is life-threatening (subject is at immediate risk of death at the time of the event; it does not refer to an event that hypothetically might have caused death if it were more severe)
- Requires in-subject hospitalization (formal admission to a hospital for medical reasons) or prolongation of existing hospitalization
- Results in persistent or significant disability/incapacity (i.e., there is a substantial disruption of a person’s ability to carry out normal life functions)
- Is a congenital anomaly/birth defect
- Is an important medical event

Important medical events that may not result in death, are not life-threatening, or do not require hospitalization may be considered an SAE when, based upon appropriate medical judgment, they may jeopardize the subject or may require medical or surgical intervention to prevent one of the

outcomes listed in this definition. Examples of such events include allergic bronchospasm requiring intensive treatment in an emergency room or at home, blood dyscrasias or convulsions that do not result in subject hospitalization, or the development of drug dependency or drug abuse.

In addition Suspected Unexpected Serious Adverse Reactions (SUSAR) may also be reported to competent authorities where this type of reporting is required (e.g. European Union Directives). See section 11.2.3.

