## 11.2 Method, Frequency, and Time Period for Detecting Adverse Events and Reporting Serious Adverse Events

Reports of AEs are to be collected from the time of study drug administration through the follow-up period ending on Day 14. The Investigator or designee must completely and promptly record each AE on the appropriate CRF. The Investigator should attempt, if possible, to establish a diagnosis based on the presenting signs and symptoms. In such cases, the diagnosis should be documented as the AE and not the individual sign/symptom. If a clear diagnosis cannot be established, each sign and symptom must be recorded individually.

The Investigator should attempt to follow all unresolved AEs and/or SAEs observed during the study until they are resolved, or are judged medically stable, or are otherwise medically explained.

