### 11.2.3 Reporting Serious Adverse Events

Any SAE / SUSAR (Suspected Unexpected Serious Adverse Reaction) must be reported to BioCryst or its designee within 24 hours of the Investigator's recognition of the SAE by first notifying the Medical Monitor at the number listed below:

Telephone: **Europe: [name]; North America: [name]**

Facsimile: **Europe: [name]; North America: [name]  
or [name]**

In addition to the telephone numbers listed above, local country-specific toll free numbers may be provided within the study reference manual.

The site is required to fax a completed SAE / SUSAR Report Form (provided as a separate report form) within 24 hours. All additional follow-up evaluations of the SAE / SUSAR must be reported and sent by facsimile to BioCryst or its designee as soon as they are available.

The Principal Investigator or designee at each site is responsible for submitting the IND safety report (initial and follow-up) or other safety information (e.g., revised Investigator's Brochure) to the Institutional Review Board/Independent Ethics Committee (IRB/IEC) and for retaining a copy in their files.

If the Investigator becomes aware of any SAE / SUSAR occurring within 30 days after a subject has completed or withdrawn from the study, he or she should notify BioCryst or its designee.

Any SAEs / SUSARs considered possibly related to treatment will be reported to the FDA and other Regulatory Competent Authorities as applicable via the MedWatch / CIOMS reporting system in accordance with FDA and other applicable regulations. However, the Investigator is not obligated to actively seek reports of AEs in former study participants.

While pregnancy is not considered an AE, all cases of fetal drug exposure via parent as study participant (see Section 4.4) are to be reported immediately to BioCryst or its designee. Information related to the pregnancy must be given on a "Pregnancy Confirmation and Outcome" form that will be provided by the Sponsor or its designee.

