Subject's oral temperature will be summarized by study visit and treatment group. Differences between the 300 mg peramivir treatment group and placebo will be assessed using the van Elteren test controlling for smoking status and positive PCR or viral culture for influenza A or B at screening. A subject has Resolution of Fever if he/she has a temperature  $< 37.2^{\circ}\text{C}$  ( $99.0^{\circ}\text{F}$ ) and no antipyretic medications have been taken for at least 12 hours. The time to resolution of fever will be estimated using the method of Kaplan-Meier using temperature and symptom relief medication information obtained from the subject diary data. Differences between the treatment groups will be assessed using the Wilcoxon-Gehan statistic controlling for smoking status and positive PCR or viral culture for influenza A or B at screening. Subjects who do not have resolution of fever will be censored at the time of their last non-missing post-baseline temperature assessment.

The number and percentage of subjects experiencing influenza related complications will be summarized by complication preferred term and treatment group. The difference between the treatment groups (300 mg peramivir and placebo) will be assessed using a Cochran-Mantel-Haenszel (CMH) test statistic controlling for smoking status, and positive PCR or viral culture for influenza A or B at screening, if applicable.

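### Section 10.1.4 keeps influenza-related complication details out of adverse event reporting without the serious-outcome exception that Section 11.1.1 gives the diary symptoms

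*Combined protocol and SAP*

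**What the plan says.** In protocol Version 4.0, Section 10.1.4 names four IRCs: sinusitis, otitis, bronchitis and pneumonia. When the investigator finds or presumes one, "he/she will record that assessment on the IRC CRF page", and any drug given for it goes on the concomitant medication page. The section then says: "Such information describing IRC signs and/or symptoms should not be reported as adverse events". No qualifier follows. The next sentence directs injection site reactions to be recorded as adverse events.

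Six other sections bear on the point.

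- Section 11.1.1 keeps the seven diary symptoms out of adverse event reporting "unless the symptom(s) worsen to the extent that the outcome fulfils the definition of an SAE", in which case they must be recorded as an SAE.
- Section 11.1.2 opens its definition with "A SAE is an adverse event that results in any of the following outcomes".
- Section 11.2 says that, where a diagnosis can be established, "the diagnosis should be documented as the AE and not the individual sign/symptom".
- Section 11.2.3 says that any SAE or SUSAR "must be reported to BioCryst or its designee within 24 hours".
- Section 10.4.2 says that "symptoms of influenza will be considered separately from adverse events".
- Section 12.7.2 counts IRCs as a secondary efficacy endpoint, which "will be summarized by complication preferred term and treatment group". The adverse event and SAE tables are specified separately in Section 12.8.

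**The concern.** Pneumonia is one of the four named complications, and it can lead to hospital admission or death. A site that takes Section 10.1.4 to mean that an IRC belongs on the IRC page and not on the adverse event page could conclude that a serious IRC never becomes an SAE. The 24-hour notice to the sponsor would then not be triggered, and the event would be missing from the SAE and treatment-emergent tables. Section 12.6 says the data monitoring committee's safety analyses follow the form of the final ones, so the committee's tables could miss it too. In a multinational study, sites could also read the sentence differently, which would make the SAE counts hard to interpret.

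The protocol recognises this danger for the diary symptoms and guards against it there. It does not do so for the complications.

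**Working it through.** No figure in the plan depends on this point, so the check is a comparison of text.

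1. **Scope of the exclusion in Section 10.1.4.** The sentence refers back to the investigator's IRC assessment and its entry on the IRC page. Its object, however, is limited to signs and symptoms. The narrow reading keeps that limit: descriptive signs and symptoms stay off the adverse event page, while the diagnosis remains reportable. The broad reading lets the back-reference carry the whole IRC off that page. The neighbouring sentence, which places injection site reactions on the adverse event side, makes the broad reading possible because the paragraph appears to be sorting one kind of record from the other.

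2. **Comparison with Section 11.1.1.** Both sections exclude expected illness findings from adverse event reporting. Section 11.1.1 restores reporting when the outcome is serious, but only for cough, sore throat, nasal obstruction, myalgia, headache, feverishness and fatigue. None of the four IRCs is on that list.

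3. **Whether another section supplies the missing exception.** Section 11.2 prefers a diagnosis to its component signs, which supports the narrow reading, but it does not mention IRCs. Section 10.4.2 sets aside only influenza symptoms and is silent on IRCs. Section 11.2.3 covers any SAE, but that presupposes the event has been classed as one.

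4. **The link to expedited reporting.** Under Section 11.1.2 an SAE must first be an adverse event. If an IRC is taken not to be an adverse event, its outcome is not tested against the seriousness criteria, and Sections 11.2.3 and 12.8 do not come into play.

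5. **What is preserved on either reading.** The event is on the IRC page, its treatment is on the concomitant medication page, and it is counted in the Section 12.7.2 summary.

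6. **Whether an amendment dealt with it.** The same sentence, without an exception, stands in all five protocol texts in the file, from August 2007 to Version 4.0.

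**The case against.** The strongest reply is that the narrow reading is the literal one. The sentence excludes signs and symptoms, not diagnoses or outcomes, and a death or hospital admission is not naturally either. Section 11.1.1 defines an adverse event broadly enough to include any IRC, Section 11.1.2 lists hospital admission and death without an IRC exclusion, and Section 11.2.3 applies to every SAE. Section 10.1.4 belongs to the evaluations chapter and can be seen as routing data to CRF pages rather than overriding Section 11. The Section 11.1.1 exception might also catch a hospitalised pneumonia through worsening cough or feverishness. Onward reporting to regulators covers SAEs considered possibly related to treatment, which a complication of influenza may often not be. Finally, the IRC page, the SAE form and the study reference manual are not in the file and may settle the matter.

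Much of this stands. The two readings are not equally strong, because only the narrow one gives full weight to the words about signs and symptoms. What it does not do is close the gap. No section applies the narrow reading to IRCs. Taken with Section 11.2, it would put every IRC diagnosis, serious or not, on the adverse event page as well, and nothing in the protocol tells sites to make that double entry. The route through a diary symptom is an inference and would not reach every IRC. The point about regulators leaves the site-to-sponsor notice and the SAE table exposed.

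**Conclusion.** The point holds as an unresolved ambiguity with a possible safety cost. A site following Section 10.1.4 as worded could leave a serious IRC out of 24-hour reporting and out of the SAE summaries. This rests on the Version 4.0 text alone; actual site practice cannot be judged from it.

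Three stronger conclusions that a reader might draw are not supported.

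- **That the protocol forbids reporting a serious IRC as an SAE.** It does not; the narrow reading is available and is the better fit to the words.
- **That serious IRCs would vanish from the data.** They would remain on the IRC page and in the IRC summary.
- **That the number of affected events can be bounded from phase 2.** Section 5.6 reports two SAEs, pyelonephritis and meningitis, among 114 + 113 + 115 = 342 treated subjects, and neither is a named IRC. From 0 of 342 one could compute a one-sided 95% upper limit of 1 − 0.05^(1/342) = 0.0087, and 0.0087 × 600 ≈ 5. That limits an expected count, not the range of events that could occur. It also assumes that phase 2 recorded serious IRCs as SAEs, and its rule is not shown. If the same unclear rule applied, the zero says nothing.

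The documents give no rate of serious IRCs, so no magnitude is stated. This is a cheap improvement that bears on patient safety.

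**What to change.** Reconcile Section 10.1.4 with Sections 11.1.1, 11.1.2, 11.2 and 11.2.3. Add one sentence to Section 10.1.4 that carries over the Section 11.1.1 exception: an IRC whose outcome meets the SAE definition is also recorded as an SAE and reported under Section 11.2.3.

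Non-serious IRCs stay on the IRC page only, and the IRC endpoint and its analysis do not change. No new data collection is needed. The one visible consequence is that some serious IRCs will appear in both the IRC summary and the SAE summary, which the table footnotes can state. If the sponsor already intended serious IRCs to be reported, the sentence simply confirms it.
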